#### **3.2.9** Global/Country Situation

Impact of global or country situation is captured in the eCRF. Impact in terms of

- Disposition (discontinued IMP or withdrew study due to global/country situation)
- Disruption (visit impact, drug impacted)

• Important Protocol Deviations (IPDs) (Subjects with at least one IPD related to global/country situation)

will be summarized descriptively based on the FAS.

### 3.2.10 Derivations of RECIST 1.1 Visit Responses

For all subjects, the RECIST tumour response data is used to determine each subject's visit response according to RECIST version 1.1. It is also used to determine if and when a subject has progressed in accordance with RECIST and their best objective response to study treatment.

Baseline radiological tumour assessments should be performed no more than 21 days before the start of study treatment and ideally as close as possible to the start of study treatment. Tumour assessment is conducted every 8 weeks ( $\pm 1$  week) after the start of treatment (Cycle 1 Day 1) up to 18 months, then every 12 weeks ( $\pm 1$  week) until objective disease progression as per RECIST 1.1, irrespective of treatment decisions. Treatment start date will only be used to determine tumour assessment schedule, date of randomisation will be used for analysis.

If an unscheduled assessment is performed, and the subject has not progressed, every attempt is made to perform the subsequent assessments at their scheduled visits. This schedule is followed in order to minimise any unintentional bias caused by some subjects being assessed at a different frequency than other subjects.

From the investigator's review of the imaging scans, the RECIST tumour response data is used to determine each subject's visit response according to RECIST version 1.1. At each visit, subjects are programmatically assigned a RECIST 1.1 visit response of CR, PR, SD or PD, using the information from TLs, NTLs and new lesions and depending on the status of their disease compared with baseline and previous assessments. If a subject has had a tumour assessment that cannot be evaluated then the subject is assigned a visit response of NE, (unless there is evidence of progression in which case the response is assigned as PD).

Please refer to Table 2 for the definitions of CR, PR, SD and PD.

RECIST outcomes (i.e. PFS, ORR etc.) are calculated programmatically for the site investigator data from the overall visit responses.

If there are patients with non-measurable disease or no evidence of disease assessed at baseline RECIST has been modified to allow the assessment of progression due to new lesions in subjects with no evidence of disease at baseline.

#### Target lesions (TLs) – site investigator data

Measurable disease is defined as having at least one measurable lesion, not previously irradiated, which is  $\geq 10$  mm in the longest diameter (LD), (except lymph nodes which must have short axis  $\geq 15$  mm) with computed tomography (CT) or magnetic resonance imaging (MRI) and which is suitable for accurate repeated measurements. A subject can have a maximum of five measurable lesions recorded at baseline with a maximum of two lesions per organ (representative of all lesions involved and suitable for accurate repeated measurement) and these are referred to as target lesions (TLs). If more than one baseline scan is recorded then measurements from the one that is closest and prior to randomisation/first dose is used to define the baseline sum of TLs. It is the case that, on occasion, the largest lesion does not lend itself to reproducible measurement. In which circumstance the next largest lesion, which can be measured reproducibly, is selected.

All other lesions (or sites of disease) not recorded as TL are identified as non-target lesions (NTLs) at baseline. Measurements are not required for these lesions, but their status are followed at subsequent visits.

Note: For subjects who do not have measurable disease at entry (i.e. no TLs) but have nonmeasurable disease, evaluation of overall visit responses are based on the overall NTL assessment and the absence/presence of new lesions (see section below for further details). If a subject does not have measurable disease at baseline then the TL visit response is Not Applicable (NA).

For subjects with no disease at baseline (i.e. no TLs and no NTLs), evaluation of overall visit responses is based on absence/presence of new lesions. If no TLs and no NTLs are recorded at a visit, both the TL and NTL visit response is recorded as NA and the overall visit response is no evidence of disease (NED). If a new lesion is observed then the overall visit response is PD.

Visit Responses	Description
Complete response (CR)	Disappearance of all TLs. Any pathological lymph nodes selected as TLs must have a reduction in short axis to <10mm.
Partial response (PR)	At least a 30% decrease in the sum of diameters of TLs, taking as reference the baseline sum of diameters as long as criteria for PD are not met.
Progressive disease (PD)	$A \ge 20\%$ increase in the sum of diameters of TLs and an absolute increase of $\ge 5$ mm, taking as reference the smallest sum of diameters since treatment started including the baseline sum of diameters.

#### Table 2TL Visit Responses (RECIST 1.1)

Visit Responses	Description
Stable disease (SD)	Neither sufficient shrinkage to qualify for PR nor sufficient increase to qualify for PD.
Not evaluable (NE)	Only relevant in certain situations (i.e. if any of the TLs were not assessed or not evaluable or had a lesion intervention at this visit). Note: If the sum of diameters meets the progressive disease criteria, progressive disease overrides not evaluable as a TL response.
Not Applicable (NA)	No TLs are recorded at baseline.

#### **Rounding of TL data**

For calculation of PD and PR for TLs percentage changes from baseline and previous minimum are rounded to one d.p. before assigning a TL response. For example 19.95% is rounded to 20.0% but 19.94% is rounded to 19.9%

#### **Missing TL data**

For a visit to be evaluable then all TL measurements are recorded. However, a visit response of PD is still assigned if any of the following occurred

- A new lesion is recorded,
- A NTL visit response of PD is recorded,
- The sum of TLs is sufficiently increased to result in a 20% increase, and an absolute increase of  $\geq$  5mm, from nadir even assuming the non-recorded TLs have disappeared.

# Note: the nadir can only be taken from assessments where all the TLs had a LD recorded.

If the TL visit response is not recorded as PD, then the TL visit response is NE.

If there is at least one TL measurement missing and a visit response of PD cannot be assigned, the visit response is NE.

If all TL measurements are missing then the TL visit response is NE. Overall visit response is also NE, unless there is a progression of non-TLs or new lesions, in which case the response is PD.

### Lymph nodes

For lymph nodes, if the size reduces to < 10mm then these are considered non-pathological. However, a size is still given and this size is still used to determine the TL visit response as normal. In the special case where all lymph nodes are < 10mm and all other TLs are 0mm then although the sum may be > 0mm the calculation of TL response should be overwritten as a CR.

#### TL visit responses subsequent to CR

Only CR, PD or NE can follow a CR. If a CR has occurred then the following rules at the subsequent visits must be applied:

- If all lesions meet the CR criteria (i.e. 0mm or < 10mm for lymph nodes) then response is set to CR irrespective of whether the criteria for PD of TL is also met i.e. if a lymph node short axis increases by 20% but remains < 10mm.
- If some lesion measurements are missing but all other lesions meet the CR criteria (i.e. 0mm or < 10mm for lymph nodes) then response is set to NE irrespective of whether the criteria for PD of TL is also met i.e. if a lymph node short axis increases by 20% but remains < 10mm.
- If not all lesions are missing, and those that are non-missing do not meet the CR criteria (i.e. a pathological lymph node selected as TL has short axis ≥ 10mm or the reappearance of previously disappeared lesion), then response is set to PD.
- If all lesions are missing the response is set to NE.

#### TL too big to measure

If a TL becomes too big to measure this is indicated in the database and a size ('x') above which it cannot be accurately measured is recorded. If using a value of x in the calculation of TL response does not give an overall visit response of PD, then this is flagged and reviewed by the study team blinded to treatment assignment. It is expected that a visit response of PD remains in the vast majority of cases.

#### TL too small to measure

If a TL becomes too small to measure then this is indicated as such on the case report form and a value of 5mm is entered into the database and used in TL calculations. However a smaller value is used if the radiologist has not indicated 'too small to measure' on the case report form and has entered a smaller value that can be reliably measured. If a TL response of PD results (at a subsequent visit) then this is reviewed by the study team blinded to treatment assignment.

#### Irradiated lesions/lesion intervention

Previously irradiated lesions (i.e. lesion irradiated prior to entry into the study) are recorded as NTLs and should not form part of the TL assessment.

Any TL (including lymph nodes), which has had intervention during the study (for example, irradiation / palliative surgery / embolization but note this does not include protocol specified biopsies), are handled in the following way. Once a lesion has had intervention then it is treated as having intervention for the remainder of the study noting that an intervention most likely shrinks the size of tumours:

- Step 1: the diameters of the TLs (including the lesions that have had intervention) are summed and the calculation is performed in the usual manner. If the visit response is PD, this remains as a valid response category.
- Step 2: If there is no evidence of progression after step 1, the lesion diameter (for those lesions with intervention) will be treated as missing and if ≤1/3 of the TLs have missing measurements then scale up as described in the 'Scaling' section below. If the scaling results in a visit response of PD then the patients will be assigned a TL response of PD.
- Step 3: If, after both steps, PD has not been assigned, then, if appropriate (i.e. if ≤1/3 of the TLs have missing measurements), the scaled sum of diameters calculated in step 2 will be used, and PR or SD will be assigned as the visit response. Patients with intervention will be evaluable for CR as long as all non-intervened lesions are 0 (or <10mm for lymph nodes) and the lesions that have been subject to intervention have a value of 0 (or <10mm for lymph nodes) recorded. If scaling up is not appropriate due to too few non-missing measurements, then the visit response will be set as NE.

At subsequent visits, the above steps are repeated to determine the TL and overall visit response When calculating the previous minimum, lesions with intervention will be treated as missing and scaled up (as per step 2 above).

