#### Overall visit response - site investigator data

Table 4 defines how the previously defined TL and NTL visit responses are combined with new lesion information to give an overall visit response. Confirmation of progression is not required.

Table 4	Overall visit responses		
TARGET	NON-TARGET	NEW LESIONS	OVERALL VISIT RESPONSE
CR	CR or NA	No (or NE)	CR
CR	Non-CR/Non-PD or NE	No (or NE)	PR
PR	Non-PD or NE or NA	No (or NE)	PR
SD	Non-PD or NE or NA	No (or NE)	SD
PD	Any	Any	PD

TARGET	NON-TARGET	NEW LESIONS	OVERALL VISIT RESPONSE
Any	PD	Any	PD
Any	Any	Yes	PD
NE	Non-PD or NE or NA	No (or NE)	NE
NA	CR	No (or NE)	CR
NA	Non-CR/Non-PD	No (or NE)	Non-CR/Non-PD
NA	NE	No (or NE)	NE
NA	NA	No (or NE)	NED

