#### 4.3.1.2 Derivations

A confirmed response of CR/PR means that a response of CR/PR is recorded at 1 visit and confirmed by repeat imaging not less than 4 weeks after the visit when the response was first observed with no evidence of progression between the initial and CR/PR confirmation visit. Data obtained up until progression, or last evaluable assessment in the absence of progression, are included in the assessment of ORR. Also only data obtained before the start of subsequent anticancer treatment (excluding radiotherapy) are included. Therefore both visits contributing to a confirmed response must be prior to progression and prior to subsequent anticancer treatment.

In the case where a subject has two non-consecutive visit responses of PR, then, as long as the time between the 2 visits of PR is greater than 4 weeks and there is no PD between the PR visits, the subject is defined as a responder. Similarly, if a subject has visit responses of CR, NE, CR, then, as long as the time between the 2 visits of CR is greater than 4 weeks, then a best response of CR is assigned.

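### The CR rule for treated target lesions has no cap and no stated order against NE, so an irradiated-only subject can be a confirmed investigator-assessed responder or NE

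*SAP*

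**What the plan says.** The rule is in Section 3.2.10 of the main-study SAP, under irradiated lesions/lesion intervention. The sub-study SAP repeats it in its own Section 3.2.10.

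- **PR and SD.** After the PD checks, and only if at most 1/3 of TLs count as missing, "the scaled sum of diameters calculated in step 2 will be used, and PR or SD will be assigned as the visit response".
- **CR, untreated lesions.** "Patients with intervention will be evaluable for CR as long as all non-intervened lesions are 0" (or under 10 mm for nodes).
- **CR, treated lesions.** In addition, "the lesions that have been subject to intervention have a value of 0 (or <10mm for lymph nodes) recorded". The sentence does not limit how many TLs may have been treated.
- **NE.** The sentence that follows reads: "If scaling up is not appropriate due to too few non-missing measurements, then the visit response will be set as NE".
- **TL response table** (Table 2 main study, Table 3 sub-study). NE applies "if any of the TLs were not assessed or not evaluable or had a lesion intervention at this visit", and only PD is named as overriding it.
- **Overall response table** (Table 4 main study, Table 5 sub-study). TL CR with NTL CR or NA gives overall CR. TL CR with NTL "Non-CR/Non-PD or NE" gives overall PR.
- **ORR data window** (4.3.1.2 main study, 4.3.5.2 sub-study). "only data obtained before the start of subsequent anticancer treatment (excluding radiotherapy) are included". Confirmation needs repeat imaging at least 4 weeks later.

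**The concern.** The SAP itself expects local treatment to reduce lesion size, "noting that an intervention most likely shrinks the size of tumours". For PR and SD it therefore sets treated lesions aside and scales from the others. For CR it accepts the recorded 0 mm of a treated lesion, whatever share of TLs was treated. If there is no untreated TL left, nothing in the CR condition tests the study drug.

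Two programmers following the text could classify the same subject as a confirmed responder or as NE. If the CR reading is taken, the effect on investigator ORR is one-directional, since it can only turn an NE subject into a responder. That matters for an ORR sensitivity analysis meant to check the primary result. It matters more directly in the sub-study, where investigator ORR is itself a secondary endpoint and Section 4.3 bases efficacy on investigator assessment.

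**Working it through.** No stated figure depends on this rule, so there is none to reproduce. The check is a trace of the rule, a count of the cases it covers, and the effect per subject.

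**1. One subject through the steps (hypothetical).** One TL of 30 mm at baseline; SD at week 8; irradiated at week 10; recorded as 0 mm at weeks 16 and 24; non-target disease Non-CR/Non-PD; no new lesion.

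- Step 1: the sum is 0 mm, so PD is not met.
- Step 2: the treated lesion counts as missing. The missing share is 1/1, above 1/3, so there is no scaling.
- Step 3, PR/SD: not available, for the same reason.
- Step 3, CR sentence: there are no untreated TLs, so that condition is met by default. The treated TL is 0 mm, so the second condition is met. TL response: CR.
- Step 3, NE sentence: scaling is not possible for lack of measurements. TL response: NE.

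Both sentences fit the same visit, and the text does not say which comes first. The Scaling section to which Step 2 refers does not appear in the document, so it cannot settle the order.

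**2. Consequence of each reading.**

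| Reading | TL | Overall (NTL Non-CR/Non-PD) | Weeks 16 and 24 together |
|---|---|---|---|
| CR sentence stands alone | CR | PR | Scans 24 − 16 = 8 weeks apart, at least 4: confirmed response |
| NE sentence governs | NE | NE | No response |

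With NTL CR or NA, the first reading gives overall CR. Radiotherapy does not close the ORR window, so both later scans count. If the same lesion were marked too small to measure, it would be entered as 5 mm. CR would then fail for a non-nodal lesion and the visit would be NE.

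**3. How many configurations exceed the PR/SD limit.** A subject has at most 5 TLs. With n TLs and m treated (1 ≤ m ≤ n), there are 1+2+3+4+5 = 15 combinations.

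- At most 1/3 treated: 1 of 3, 1 of 4, 1 of 5, so 3 combinations.
- More than 1/3 treated: 15 − 3 = 12, including every case with 1 or 2 TLs.
- All TLs treated (m = n): 5 of those 12. Here the untreated-lesion condition is empty.
- In the other 12 − 5 = 7, at least one untreated TL must also have disappeared.

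**4. Size per subject.** Added ORR = 1/n. Combination arm: 1/100 = 1.0 point. Monotherapy arm: 1/50 = 2.0 points. With assumed responder counts (not from the SAP) and two-sided 95% Clopper-Pearson intervals:

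| n | Responders | ORR | 95% CI |
|---|---|---|---|
| 100 | 10 | 10.0% | 4.9 to 17.6 |
| 100 | 11 | 11.0% | 5.6 to 18.8 |
| 100 | 13 | 13.0% | 7.1 to 21.2 |
| 50 | 2 | 4.0% | 0.5 to 13.7 |
| 50 | 3 | 6.0% | 1.3 to 16.5 |
| 50 | 5 | 10.0% | 3.3 to 21.8 |

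For the sub-study no such figure can be given: ORR uses the Safety analysis set, and planned enrolment is redacted.

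**The case against.** The strongest reply is that the NE sentence and the NE row of the TL response table already block the problem. Both can be read that way, so it would be wrong to say the SAP plainly grants CR without limit. But the NE sentence speaks of cases where scaling fails, and CR needs no scaling, so the CR sentence can also be read as a separate allowance. The table row conflicts with Step 3 even for PR and SD, so it does not settle the order. What stands is an unresolved order rather than a clear permission.

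A second reply is that the 1/3 limit belongs to scaling, and CR uses recorded values, so the different treatment has a reason. That explains the drafting, but not why a treated lesion's 0 mm should count when no untreated TL exists.

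Stronger readings that a reader might infer, and that the documents do not support:

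- **The primary result is biased.** Primary ORR is by BICR, and Section 4.3 says BICR visit responses need no programmatic derivation. The 4% and 10% chemotherapy rates in Section 3.2.1 belong to the success rationale for that endpoint and are not a yardstick for this effect.
- **Every investigator BOR is affected.** The BOR text (4.3.2 main study, 4.3.6 sub-study) stops at any subsequent cancer therapy and has no radiotherapy exemption.
- **Resection creates responders in the same way.** Only radiotherapy is exempted from the ORR cut-off; the status of surgery and embolisation is not stated.
- **One subject moves sub-study ORR by 1/30.** About 30 is the target for evaluable paired biopsies, not the ORR denominator.
- **Local therapy alone is enough in any treated subject.** It is enough only where all TLs were treated, with no new lesion and no NTL progression, on two scans.

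**Conclusion.** The point holds in a limited form. The CR sentence lacks the limit that applies to PR and SD, and its order against NE is not stated. On one permissible reading, irradiation of the only TL, or of all TLs, yields a confirmed investigator-assessed response; on the other reading the same subject is NE.

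The reach is investigator-based ORR and the DoR and TTR that depend on it: sensitivity and investigator interim response analyses in the main study, and secondary endpoints in the sub-study. The size is one responder per such subject, or 1 point at n=100 and 2 points at n=50. The total cannot be estimated, because the documents do not say how often TLs are irradiated on study, and the conditions are narrow. It is worth settling because it is cheap and the possible error in ORR runs one way.

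**What to change.** In Step 3 of both SAPs, replace the CR and NE sentences with one ordered rule, applied once PD has been excluded:

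1. CR may be assigned only if at most 1/3 of TLs have had an intervention and all TLs, treated and untreated, are 0 mm (or under 10 mm for nodes).
2. If at most 1/3 have been treated and CR is not met, assign PR or SD from the scaled sum, as now.
3. If more than 1/3 have been treated, the TL response is NE.

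The second line is needed so that the NE fallback does not remove PR and SD from subjects within the limit. Then align the NE row of the TL response table (Table 2 main study, Table 3 sub-study) with this order.

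The cost is a short text change in each SAP and one programming condition. A few subjects may move from CR or PR to NE, including some with an untreated TL that did disappear (for example 1 of 2 treated), so investigator ORR may be slightly lower. Within the limit (1 of 3, 4 or 5 treated) the treated lesion's 0 mm still counts, but at least two untreated TLs must then also have disappeared.

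### After local treatment of a target lesion, Step 1 as written sets an unscaled sum against a scaled previous minimum, so unchanged disease can be called PD when the treated lesion lags the others

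*SAP*

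**What the plan says.** The rule is in Section 3.2.10 of the main-study SAP, under Irradiated lesions/lesion intervention, and is repeated in Section 3.2.10 of the biopsy sub-study SAP.

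- Step 1: "the diameters of the TLs (including the lesions that have had intervention) are summed and the calculation is performed in the usual manner". On the outcome: "If the visit response is PD, this remains as a valid response category".
- Step 2 is reached only if Step 1 shows no progression. The treated lesion is then set to missing and, if no more than a third of the target lesions are missing, the plan says "then scale up as described in the 'Scaling' section below". No section of that name follows in either SAP.
- Step 3 assigns PR or SD from the scaled sum where scaling is possible.
- For later visits: "At subsequent visits, the above steps are repeated to determine the TL and overall visit response". The reference is then defined: "When calculating the previous minimum, lesions with intervention will be treated as missing and scaled up (as per step 2 above".

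Three other rules bear on this. The PD definition in the target-lesion response table requires at least +20% and +5 mm, "taking as reference the smallest sum of diameters since treatment started including the baseline sum of diameters". The rounding rule says "percentage changes from baseline and previous minimum are rounded to one d.p. before assigning a TL response". The note under Missing TL data says "the nadir can only be taken from assessments where all the TLs had a LD recorded", which does not fit easily with a minimum built from a lesion set to missing.

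**The concern.** Step 1 is repeated at every later visit, and the sentence on the previous minimum follows it with no exception. The quantity tested then includes the treated lesion, while the quantity it is tested against does not. If the untreated lesions have shrunk clearly more than the treated one, the first exceeds the second without any growth. Steps 2 and 3 cannot correct the call, because they run only when Step 1 has not found PD.

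A false PD at the scan that should confirm a response leaves that response unconfirmed and creates a PFS event. If the response was already confirmed, ORR is unaffected, but DoR and PFS are cut short.

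**Working it through.** The plan gives no figure to reproduce, so the steps are applied to worked lesion sets. The scaling rule is not given. The assumed range is (a) by share of the baseline sum and (b) by share at the pre-treatment nadir. Scaling by lesion count gives the same values as (a) where baseline lesions are of equal size.

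**Main example, rule (a).** Baseline 30/30/30 = 90 mm; third lesion irradiated before week 8.

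1. Week 8, 15/15/30. Step 1: 60 against 90 mm, no PD. Step 2: the untreated lesions are at 30/60 = 0.5 of baseline, so the scaled sum is 0.5 × 90 = 45 mm, which is -50% and PR.
2. Week 16, unchanged. The previous minimum as written is 45 mm. Step 1: 60 against 45 mm = 60/45 - 1 = +33.3%, +15 mm, PD.
3. Like for like: 60 against 60 mm, or 45 against 45 mm, is 0%. The PR would be confirmed.

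The pre-treatment nadir here is baseline itself, so rule (b) also gives 45 mm.

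**General condition, rule (a).** Let B be the baseline sum, w the treated lesion's share of it, r the treated lesion's size relative to its baseline, and R the same ratio for the untreated lesions. With nothing changing:

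- unscaled sum = B[(1 - w)R + wr]; scaled minimum = BR
- ratio = (1 - w) + w·r/R, which reaches 1.20 when r/R ≥ 1 + 0.2/w
- absolute difference = Bw(r - R), which must be at least 5 mm

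The threshold for r/R is 1 + 0.6 = 1.6 at w = 1/3, 1 + 0.8 = 1.8 at w = 1/4, and 1 + 1.0 = 2.0 at w = 1/5. In the main example r/R = 1/0.5 = 2.0 and the difference is 90 × 1/3 × 0.5 = 15 mm, so both criteria are met.

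**Other cases, all from baseline 50/50/50 mm with the third lesion treated.** Step 1 is shown at the second post-treatment scan, with visits before treatment left unscaled.

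| Course | Rule | Sum against minimum (mm) | Change | Call |
|---|---|---|---|---|
| 27.5/27.5/45 held | (a) | 100 v 82.5 | +21.2%, +17.5 mm | PD |
| 10/10/40 held | (a) | 60 v 30 | +100%, +30 mm | PD |
| 10/10/40 held, reached before treatment | (b) | 60 v 60 | 0% | not PD |
| 20/20/40 before treatment, 10/10/40 twice after | (b) | 60 v 40 | +50%, +20 mm | PD |
| 25/25/25 held | (a) | 75 v 75 | 0% | not PD |
| 25/25/40 before treatment, 25/25/10 twice after | (a) | 60 v 75 | -20% | not PD |
| same | (b) | 60 v 90 | -33.3% | not PD |

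Under (b), then, a false PD needs the untreated lesions to shrink further after treatment and then hold.

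**Timing.** In the 10/10/40 case under (a), the first post-treatment scan gives 60 against 60 mm and is not PD; the false call comes one scan later. If visits before treatment are also re-scaled, the minimum is already 30 mm and PD falls at the first post-treatment scan. The plan does not say which applies.

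**Matched comparison.** With the unscaled sum set against the unscaled minimum in Step 1, every example in which the lesions are unchanged gives 0% and no PD.

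**The case against.** The best defence is that Step 1 is to be calculated the ordinary way. The ordinary reference is the smallest recorded sum, and the closing sentence refers back to Step 2, so the scaled minimum may be meant only for the scaled steps. That reading is coherent and may be what was intended. The text does not state it, however, and the more specific sentence about the minimum comes straight after the instruction to repeat all the steps. Two programmers could code it differently.

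It is also fair that the SAP expects a local intervention to shrink the lesion, in which case the problem does not arise, and that the result depends on a scaling rule that is not shown. Both points narrow the concern without removing it.

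Some stronger readings are tempting and are not supported:

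- A reader might infer that any responder with stable lesions is called PD after local treatment. That needs the treated lesion to lag by the margins shown above.
- A reader might infer that Step 1 has no reference once more than a third of the lesions are treated. Baseline and other sums from before the intervention remain available, and nothing says they are discarded.
- A reader might want a misclassification rate. The documents give no distribution of lesion changes and no frequency of local treatment.
- A reader might use the roughly 30 patients with paired biopsies as the sub-study's response denominator. That is a biopsy target; ORR there uses the safety analysis set.

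**Conclusion.** The rule is wrong as written in both SAPs. Followed literally, it can assign an irreversible PD to a subject whose lesions have not changed, when the treated lesion has shrunk clearly less than the others. Under baseline-share scaling the threshold is a relative-size ratio of 1.6 to 2.0 for a treated share of 1/3 to 1/5, plus the 5 mm criterion. Under nadir-share scaling the error is confined to further shrinkage of untreated lesions after treatment that then holds.

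The reach is limited. Main-study visit responses from central review are not derived by this algorithm, so the primary ORR is untouched. What is exposed is the investigator-based sensitivity analyses (for example Sections 4.3.1.5, 4.3.5.5, 4.3.6.5 and 4.3.9.5), the investigator-versus-central comparison in Section 4.3.9.6, and the sub-study's secondary tumour endpoints. The last rest on investigator data alone; the sub-study's primary endpoint, CD8+ infiltration, is not affected. Few subjects are likely to have a treated target lesion. The point is worth correcting because the correction is cheap and the error, where it occurs, falls on responders.

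**What to change.** In Section 3.2.10 of both SAPs:

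1. State that Step 1 compares the recorded, unscaled sum of all target lesions with the smallest earlier recorded, unscaled sum, baseline included.
2. Limit the sentence on the previous minimum to Steps 2-3, and require the scaled sums to be compared over the same untreated lesions, scaled the same way.
3. Supply the missing scaling rule, say whether visits before the intervention are re-scaled, and reconcile the result with the nadir note under Missing TL data.

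The cost is a few sentences in each SAP and one extra stored minimum in the derivation program; no new data are needed.

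There is one small downside. Regrowth of a treated lesion from a nadir lowered by the intervention will count as PD in Step 1. For example, with baseline 30/30/30, 30/30/0 (60 mm) followed by 30/30/12 (72 mm) is +20% and +12 mm, whereas against a scaled minimum of 90 mm it is -20%. This is the plan's ordinary PD rule applied to recorded sums, and it should be accepted knowingly.
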